15.2 Qualitative analysis

Interviews will be recorded with the consent of participants and transcribed verbatim and anonymised by a professional transcription company. Interview transcripts will be quality-checked and uploaded to NVivo 12 for analysis. Thematic analysis will be used to identify key patterns in the interview data. This will consist of a series of steps: familiarisation with data, generating initial codes, and searching, reviewing and defining themes. Themes that relate to the objectives of the research will be identified, but analysis will also allow new themes generated by interviewees to be identified. A proportion of the transcripts will be double-coded, and the thematic framework will be discussed and refined by the trial qualitative researchers. Full details of the analysis will be included in the qualitative analysis plan (QAP).

15.3 Cost-effectiveness analysis

A health economic evaluation will provide evidence of the relative costs and outcomes of these common antithrombotic strategies to inform future decision-making. The evaluation will be designed, conducted and reported following best-practice guidelines conforming to the Consolidated Health Economic Evaluation Reporting Standards (44).

A UK NHS/Personal Social Services Perspective will be taken for the base case. Acknowledging the wider economic impact of CLTI and its treatments, a restricted societal perspective will report the additional costs to patients and carers (e.g. out-of-pocket expenses for travel) alongside capture of time away from usual activities (such as work) as part of a supplementary analysis.

Resource use and costs:

We will collect information from trial records and patient-reported outcome measures to assess resource use as part of the CLARITY data collection schedule (see Table 2). We will use an adapted CSRI to capture resource use. We will work with the CLARITY PPI group and research team to develop this during the trial set-up to ensure we capture the key drivers of resource use associated with the use of the different antithrombotic strategies (e.g. hospital re-admission related to an adverse event), balanced with the need for a proportionate measure to minimise patient and researcher burden in the collection of resource use.

We will use published UK unit costs to value resource use in £ sterling to the most relevant price year available at the time of final analysis. We will present the total and per-participant costs associated to produce a comprehensive summary of resource use and associated costs associated with the intervention and comparator groups.

Health outcomes:

The EQ-5D-5L will be used in the economic analysis, with the schedule for data collection and approach summarised in Table 2. This has been chosen as it is the preferred measure for capturing HRQOL in adults by NICE. We will use the most appropriate method recommended at the time of analysis to derive utilities for a UK population (e.g. pending completion of the new UK 5L valuation set or using a 5L-3L cross-mapping function) (45). With the use of the VascuQoL-6 as a condition-specific measure of HRQOL within CLARITY, we will use this measure to present a secondary cost-effectiveness analysis.

Primary analysis:

A cost-utility analysis will be conducted based on the follow-up of 36 months of the ITT population alongside a secondary analysis at 12 months to assess the short and longer-term cost-effectiveness of the antithrombotic strategies. Discounting at 3.5% will be applied to costs and outcomes beyond 12 months. A within-trial analysis will be conducted.

We will consider the feasibility of undertaking an economic model to extrapolate costs and outcomes beyond the three-year time horizon based on the trial findings and the plausibility of making longer-term estimations from robust literature input available (e.g. systematic reviews) and/or clinical expert opinion. We will undertake a rapid review of relevant literature (including UK HTA reports from NICE) to identify potential models and decide on a suitable model structure. Whilst we expect this to be a relatively simple model (e.g. decision tree and/or Markov), we will make the final decision (e.g. whether a more complex simulation model is necessary) as part of developing our health economic analysis plan Our analysis plan will be prepared in collaboration with the CLARITY research team alongside the development of the SAP. As required, the final economic analysis plan will follow the decisions made following the adaptive interim analysis proposed in CLARITY. We will use consistent methods to produce the within-trial analysis and, if applicable, inform the model e.g. cost and outcome inputs.

An adjusted analysis using suitable regression models will be performed to calculate incremental costs and quality-adjusted life years (QALYs). The pattern of missing data (e.g. missing at random) will be examined and accounted for by suitable methods such as multiple imputation (MI) for missing

observations of cost and EQ-5D 5L measure. Imputed data based on the ITT population will be used for the base-case analysis for both analyses. An incremental cost per QALY gain at 12 and 36 months for each antithrombotic strategy included in the final analysis will be calculated, with the presentation of incremental net monetary benefit. We will use appropriate decisions such as identifying dominant strategies (if all strategies remain in the final analysis) in reporting our findings. Consistent with the statistical analysis, alternative analysis populations will be used. Any modelling of costs and outcomes beyond the trial time horizon will be exploratory analysis.

Deterministic and probabilistic sensitivity analyses will be conducted to explore the uncertainty in our findings from our cost-utility analysis. Cost-effectiveness acceptability curves will be presented to consider which optimal antithrombotic strategy represents value for money, based on a societal threshold of £20,000-£30,000 per QALY gain. A secondary cost-effectiveness analysis will be undertaken to assess the incremental cost-per-point improvement in VascuQoL-6 score.

16 Data Management

Source data is defined as "All information in original records and certified copies of original records of clinical findings, observations or other activities in a clinical trial necessary for the reconstruction and evaluation of the trial. Source data are contained in source documents."

There is only one set of source data at any time for any data element, as defined in the site source data agreement. The source data for CLARITY will be from a variety of sources as described in Table 2.

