N/A	1.0		First version

2 Synopsis

Short title	Clopidogrel, Aspirin and Rivaroxaban after revascularisation with angioplasty for limb-threatening Peripheral Arterial Disease		
Acronym	CLARITY PAD		
Internal ref. no.	UID 948		
Clinical phase	Phase IV		
Funder and ref.	NIHR HTA 154252		
Trial design	Pragmatic, adaptive multicentre open-label three-arm individually randomised controlled trial (RCT)		
Trial participants	Adults undergoing percutaneous or hybrid endovascular intervention for Chronic Limb Threatening Ischemia (CLTI)		
Planned sample size	1,239		
Planned number of sites	Around 20		
Inclusion criteria	 Adults (aged 18 years and over) undergoing percutaneous or hybrid endovascular intervention for CLTI of the lower limbs Atherosclerosis as the cause of CLTI Target arteries: infrainguinal (common femoral to pedal) if percutaneous, or iliac to pedal if performed as part of hybrid revascularisation with common femoral endarterectomy Clinicians would use trial antithrombotic combinations in normal clinical practice Able to provide informed consent First time in the CLARITY trial 		
Exclusion criteria	 Open bypass as part of hybrid procedure Intervention for asymptomatic restenosis of a bypass graft Pre-existing indication for dual antiplatelet therapy or anticoagulant e.g. atrial fibrillation Active malignancy or any other non-vascular condition associated with a life expectancy of less than 36 months Embolic arterial disease Renal failure with creatinine clearance <15ml/minute Thrombophilia or any other inherited or acquired bleeding disorder Persons of childbearing potential who have a positive pregnancy test, are breastfeeding or attempting pregnancy 		
Treatment duration	12-36 months		
Follow-up duration	Up to 36 months		
Planned trial period	01 January 2024 – 01 January 2029		
Primary objective	To compare the clinical effectiveness of three commonly used antithrombotic regimens (clopidogrel; aspirin plus clopidogrel; aspirin plus low-dose rivaroxaban) following endovascular intervention for CLTI		
Secondary objectives	 To evaluate the clinical and cost-effectiveness of clopidogrel; aspirin plus clopidogrel; aspirin plus low-dose rivaroxaban following endovascular intervention To evaluate the delivery of the CLARITY trial and trial interventions 		

Tertiary/Exploratory objectives	To explore how the trial interventions work in the real healthcare system
Primary outcomes	Primary effectiveness outcome: A composite event-free survival time of:

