We published a survey of 162 UK consultants in 2019 which showed equipoise between dual antiplatelet therapy (aspirin plus clopidogrel 50%) and single antiplatelet therapy (clopidogrel or aspirin, 37%) following endovascular intervention (9). We repeated the survey in 2022 with 52 responses covering most UK vascular units. The majority of practice was clopidogrel alone (46%), dual antiplatelet therapy with aspirin plus clopidogrel (27%) and aspirin plus low-dose rivaroxaban (6%). These are also the drug choices with weak guideline recommendations (15,16) and therefore constitute our trial arms. Aspirin plus low-dose rivaroxaban will likely become more widely adopted with time after the publication of VOYAGER in 2020. To what extent this will happen is unclear as, despite a large marketing push from the company, clinical use has been limited as shown by our questionnaires. 90% of vascular surgeons still thought there was insufficient evidence to guide practice and 94% said they were willing to randomise patients in an RCT. A further survey was performed in December 2022 as part of reassuring the National Institute of Health Research (NIHR) funding panel on feasibility. Sixty-seven responses from vascular consultants in 47 UK vascular centres were received, with the same results as the previous questionnaire.

Combining the results of the literature review, questionnaire and patient and public involvement (PPI) work (outlined in subsequent sections) led to the 3-arm design and choice of antithrombotics.

Current guideline recommendations:

There is no formal National Institute for Health and Clinical Excellence (NICE) guidance in this area, only technology appraisal guidance for rivaroxaban (17) and clopidogrel (18). This is in stark contrast to cardiology (endovascular coronary intervention which is similar to endovascular lower limb intervention) where there are multiple large RCTs and detailed NICE guidance as a result (19). Other PAD guidelines can only make weak recommendations for antithrombotics after endovascular intervention due to the lack of data (15,16). Rivaroxaban 2.5mg is still on patent and is significantly more expensive than clopidogrel (rivaroxaban 2.5mg NHS tariff £1.80/day, clopidogrel £0.05/day).

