15.1.1 Sub-group & interim analysis

A planned interim analysis of the co-primary outcomes will be conducted when 60% of the planned maximum number of primary outcome events have been observed. The interim analysis will compare each of the combination arms against the clopidogrel-only arm (which has the lowest predicted clinical effectiveness) using futility-stopping criteria based on conditional or predictive power which leads to minimal overall power loss. These criteria will be finalised during the trial set-up phase and fully specified in the SAP.

If the futility of the clopidogrel-only arm is shown in at least one of the two comparisons, the trial will continue with the two combination arms only. Participants in the futile arm will continue with the allocated drug and will be followed up until the end of the trial. If all three arms continue through to the final analysis, each of the combination arms will be compared to clopidogrel only, each at 2.5% alpha. If only one is significantly better, it will be declared the most effective. If both combination therapy arms are significantly better, they will then be compared against each other using the full 5% alpha, thus ensuring strong control of the familywise type I error rate.

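### If the interim closes clopidogrel alone, section 15.3 as worded takes it out of the incremental cost-effectiveness analysis, at odds with its own all-randomised base case

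*Protocol*

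**What the plan says.** Section 15.3 contains four statements that bear on which regimens are compared.

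- The incremental cost per QALY at 12 and 36 months "for each antithrombotic strategy included in the final analysis will be calculated".
- Identifying dominant strategies is conditional: "if all strategies remain in the final analysis".
- As required, "the final economic analysis plan will follow the decisions made following the adaptive interim analysis proposed in CLARITY".
- "Imputed data based on the ITT population will be used for the base-case analysis for both analyses". Sections 14.7 and 15.1 define ITT as everyone randomised with non-zero follow-up time.

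Section 15.1.1 sets the interim decision. Each combination is compared with clopidogrel alone, and futility of clopidogrel in either comparison is enough to continue with the two combinations only. "Participants in the futile arm will continue with the allocated drug and will be followed up until the end of the trial".

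The synopsis gives as a secondary objective: "To evaluate the clinical and cost-effectiveness of clopidogrel; aspirin plus clopidogrel; aspirin plus low-dose rivaroxaban following endovascular intervention". Section 4.1 gives prices ("rivaroxaban 2.5mg NHS tariff £1.80/day, clopidogrel £0.05/day") and the 2022 survey of practice: clopidogrel alone 46%, aspirin plus clopidogrel 27%, aspirin plus rivaroxaban 6%.

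**The concern.** The interim rule is about clinical effectiveness and has no cost or QALY element. Lower effectiveness is no reason to take a cheaper option out of an incremental economic analysis, because that is the option the dearer ones must be ranked against. Section 15.3 nevertheless lets the interim decide which strategies are ranked, and the only strategy it can remove is the one with the lowest drug cost.

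If clopidogrel closes, the trial would not report whether moving a patient from clopidogrel alone to either combination is worth its cost. Section 4.1 raises this question itself when it says rivaroxaban may not be cost-effective against dual antiplatelet therapy or clopidogrel alone. Because one comparison is enough, a combination never shown to be better than clopidogrel could also stay in and be judged only against the other combination.

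**Working it through.** **1. What the wording implies.** Section 15.1.1 speaks of all three arms continuing through to the final analysis, meaning arms that survive the interim. Section 15.3 uses the same term for strategies that are included or remain. A strategy can remain only if it could have left, and only clopidogrel alone can leave. The natural reading therefore omits a closed clopidogrel arm. The ITT base case in the same section points the other way, since it covers everyone randomised. The two statements do not fit together.

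**2. Whether the data would exist.** Inputs from section 14.3: 65.0% event-free at 12 months on clopidogrel, hazard ratio 0.65, 8% loss per year, accrual 25/35/40% over three years, 413 per arm.

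- Hazards per year: clopidogrel −ln(0.65) = 0.431; combinations 0.65 × 0.431 = 0.280; loss −ln(0.92) = 0.083.
- Event probability for follow-up f: λ/(λ+δ) × (1 − exp(−(λ+δ)f)), averaged over entry times.
- Check against the plan: at month 36 this gives 0.3801 × 413 = 157.0 and 0.2768 × 413 = 114.3 per combination, 385.6 in all. The plan states 157, 115 and 387, so its figures reproduce.
- Interim trigger: 0.60 × 387 = 232 events, reached at about month 28 (2.315 years).
- Share randomised by then: 0.25 + 0.35 + 0.40 × 0.315 = 0.726. On clopidogrel: 0.726 × 413 ≈ 300. If closing the arm took a further three months (an assumption), 413 × 0.40 × 0.25 ≈ 41 more, about 341.
- Follow-up ends at month 48 (section 15.1), so these participants could have at least 48 − 28 = 20 months of follow-up, or 17 for the last entrant after a three-month delay. All can reach the 12-month analysis, death and loss apart.
- Only those randomised in the first 12 months can reach 36 months: 0.25 × 413 ≈ 103 per arm, all before the interim. Closure therefore costs no potential 36-month completers on clopidogrel.

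**3. Drug cost by regimen.** Inputs: £0.05 and £1.80 per day (section 4.1); aspirin price a per day, not given; 36 months = 1,095 days; full adherence; undiscounted.

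- Clopidogrel alone: 0.05 × 1,095 = £54.75.
- Aspirin plus clopidogrel: £54.75 + 1,095a.
- Aspirin plus rivaroxaban: 1.80 × 1,095 + 1,095a = £1,971 + 1,095a.

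At these tariffs clopidogrel alone has the lowest drug cost for any positive a.

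**4. Which contrasts are lost and which stay.**

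| Contrast | Drug-cost difference, 36 months | If clopidogrel closes |
|---|---|---|
| Aspirin + clopidogrel v clopidogrel | 1,095a | lost |
| Aspirin + rivaroxaban v clopidogrel | £1,916 + 1,095a | lost |
| Aspirin + rivaroxaban v aspirin + clopidogrel | £1,916 (aspirin cancels) | kept |

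If a lies between £0.01 and £0.10 (an assumption), 1,095a is £11 to £110, and the second row is £1,927 to £2,026. Discounted at 3.5% per year after the first, £1,916 becomes 638.75 × (1 + 1/1.035 + 1/1.035²) ≈ £1,852.

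**The case against.** **The exclusion is inferred.** No sentence says that clopidogrel is removed, and the ITT base case, the continued follow-up and the objective all keep it in. A reader might infer that the clopidogrel data would simply be collected and discarded. The documents do not support anything so categorical. What stands is a conflict: an all-randomised population beside a list of strategies that the interim sets.

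**The size can be misread.** A reader might take £1,916 (0.096 QALY at £20,000 or 0.064 at £30,000) as the test that would go unmade. That is wrong, because the same gap separates the two combinations and is still tested. The figure also ignores savings from events avoided and treatment shorter than 36 months, and section 4.1 puts rivaroxaban's patent expiry in 2026, so the price may change.

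**Current practice is not lost altogether.** A reader might infer that no comparison with current practice would be left. Aspirin plus clopidogrel was 27% of practice in 2022 and 50% in the 2019 survey, when all single antiplatelet therapy was 37%. The comparison between combinations is therefore itself one with current practice. Only the step up from clopidogrel alone goes unanswered.

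**The detail belongs to the economic plan.** Section 15.3 defers to a health economic analysis plan, links it to the interim only as required, and offers dominance as an example. Acceptability curves carry no condition. This answers part of the point, but net monetary benefit sits in the same sentence as the restriction. The protocol also states that restriction outright and sends the later plan in its direction, so this is more than missing detail.

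**Conclusion.** The concern holds as a conflict within section 15.3 and as a poor rule on its natural reading. If clopidogrel alone closes, neither combination would be compared with it on incremental cost-effectiveness, although about 300 of the 413 planned clopidogrel participants would already be randomised and still followed. The lost contrasts differ in drug cost by aspirin alone, and by about £1,916 plus aspirin; the comparison between the combinations stays.

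This rests on the planned event and accrual rates, both combinations at a hazard ratio of 0.65, current tariffs, full adherence and no discounting. Lowest cost is shown for drug price only, since total cost is what the trial will measure. Most used refers to the 2022 survey. The point matters only if clopidogrel closes. Its probability cannot be given, because the futility criteria are left to the SAP.

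**What to change.** State in section 15.3 that all three randomised regimens stay in the base-case incremental analysis whatever the interim decides. This should cover ranking by cost, dominance and extended dominance, net monetary benefit and acceptability curves. Delete the two phrases that limit the analysis to strategies in, or remaining in, the final analysis.

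If clopidogrel closes early, make the three-way ranking in one common set: participants randomised while all three arms were open. Using concurrent participants only for the clopidogrel contrasts, and everyone for the contrast between combinations, would mix increments from different samples that need not agree. Report the combination contrast in all randomised participants as an additional analysis.

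The cost is wording in section 15.3 and the health economic analysis plan, and no new data. The ranking loses some precision: with about 300 per arm in place of 413, standard errors are about √(413/300) = 1.17 times as large, before missing data. Making the change before the interim also means the comparators are not chosen after results are seen.

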16.1 Data collection

Data will be collected using an electronic CRF system with paper CRF backup for PROMs. Training for completion of trial CRFs will be provided to the appropriate trial staff before trial commencement at site initiation.

Data collection data will be captured by sites in real-time as events arise as well as at fixed points by request of the trial team.

16.2 Completion of Case Report Forms (CRFs)

All data collection will be completed using web-based CRFs, held on a secure encrypted system hosted by Cardiff University. It is accessed by username and password and complies with the General Data Protection Regulation 2016. If the web-based system is not accessible, the data will be inputted by local site staff once it is accessible. A full Data Management Plan (DMP) for the CLARITY trial will accompany this protocol and will be stored in the TMF.

The trial's DMP provides an overview of the data management process to be applied to the trial to assure data quality. The DMP will:

- Define the different types of data collection documents used
- Define the procedures by which data will be collected, entered, verified and cleaned
- Define the procedures to securely manage and store the data
- Define requirements for the retention of trial data
- Describe the processes and data security measures involved in data linkage with NHS England (formerly NHS Digital) datasets

16.2.1 Electronic CRFs

The system can be accessed on:

https://clarity.ctr.cardiff.ac.uk

A user password will be supplied to investigators upon completion of all processes required prior to opening. Site staff will only have access to their participants and not see other sites' participants. Webbased data collection forms should be completed as described in the CLARITY Site Manual.

Electronic tablets will be made available to recruiting sites to facilitate direct data entry into the trial database.

16.2.2 Paper CRFs

Paper CRFs will be used for PROs if the electronic database is not available, or if participants prefer follow-up via post. Data will then be entered into the database by site staff at a later point. In accordance with the principles of GCP, the PI is responsible for ensuring the accuracy, completeness, legibility and timeliness of the data reported to the CTR in the CRFs.

CRF pages and data received by the CTR from participating trial sites will be checked for missing, illegible or unusual values (range checks) and consistency over time.

If missing or questionable data are identified, a data query will be raised on a data clarification form. The data clarification form will be sent to the relevant participating site. The site shall be requested to respond to the data query on the data clarification form. The case report form pages should not be altered.

All answered data queries and corrections should be signed off and dated by a delegated member of staff at the relevant participating site. The completed data clarification form should be returned to the CTR and a copy retained at the site along with the participants' CRFs.

The CTR will send reminders for any overdue data. It is the site's responsibility to submit complete and accurate data in a timely manner. Further details of data management procedures can be found in the CLARITY DMP.

